Second Survey (Post-Intervention) in the ED: We will administer a short survey approximately one hour after the intervention (after all 3 platforms). See SECOND SURVEY: INTERVENTION GROUP.

Complete Master Data Flow Log after each patient enrolled.

NOTE: All of the above study procedures should be performed in patient waiting times and not interfere or disrupt patient care in any way.

-

Study Procedures: Non-Intervention Blocks

The anticipated flow of the study during **Non-Intervention Blocks** is summarized in Figure 1.

Figure 2: Non-Intervention Blocks Study Flow

PROCOVAXED Trial Workflow on Non-Intervention Blocks

Introduction to ED Staff: Clinical Research Coordinators (CRCs) will set up their workstation in the ED and introduce themselves to ED staff (nurses, physicians and mid-levels), informing them that they will be doing the PROCOVAXED study that day.

CRCs will avoid telling providers intervention vs non-intervention arms.

Initial Screening and Scripted Consent for Surveys: CRCs will review ED dashboards for inclusion and exclusion information. When an eligible patient is identified, the CRC will ask the nurse or doctor caring for the patient whether it is Ok for them to approach the patient about the first survey. Whenever possible, the CRC will ask the provider to first ask the patient if they may speak to them.

For provider approved patients: CRCs will approach eligible patients and deliver a scripted consent for two short surveys: the Non-Intervention FIRST SURVEY and the Non-Intervention SECOND SURVEY. See Scripted Consent for the Non-Intervention periods.

CRCs will complete screening and enrollment log indicating whether or not they agreed to this survey. If they agreed to survey, CRC will assign a Study ID# and proceed to Master Data Flow form.

First Survey in the ED: For patients agreeing to the above surveys, we will administer a short survey – a baseline survey to be complete after obtaining scripted consent at the beginning of their ED visit (before exposure to the messaging platform intervention – PROCOVAXED FIRST SURVEY). CRCs will have the option of inputting surveys to REDCap on iPads in real time or using paper surveys (and later inputting into REDCap).

These surveys are to be delivered orally (CRC asks questions), not via handing them out. First Surveys are the same for intervention and non-intervention blocks.

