Second Survey in the ED: We will administer a second short survey at some time (approximately 1 hour) after the FIRST SURVEY. See SECOND SURVEY: NON-INTERVENTION GROUP. These second surveys in the non-intervention group have the same key primary and secondary outcome questions as in the INTERVENTION GROUP second surveys. SECOND SURVEY: NON-INTERVENTION GROUP.

NOTE: All of the above study procedures should be performed in patient waiting times and not interfere or disrupt patient care in any way.

- **Research Staff Informing of ED Providers when Participants will accept Covid vaccine**

At this time all of our EDs have the capability of administering COVID19 vaccines in some manner, and we expect that this will continue for at least the first 6 months of the trial. The last question in the SECOND SURVEY **in both arms** of the study is “Would you accept the Covid vaccine in the emergency department today if your doctor asked

you?" When a participant says they will accept the vaccine, the CRC or research staff will ask the patient if they can notify the patient's providers (nurse and/or physician) that they said they will accept the vaccine. They will also ask the patient if they (the CRC) can check to see if the patient receives the vaccine in the ED.

Other than this question and notification, research staff will not push that they get vaccinated.

- **Consent for 1- Month Follow Up Surveys for patients saying No to Vaccine in ED**

For all patients saying **no** to the question "*Would you accept the Covid vaccine in the emergency department today if your doctor asked you?*", research staff will ask if they can contact them and review their records in a month for follow up via full written consent. If patient says yes, then the CRC will get full **written** informed consent, including a separate HIPAA form, for review of their records and phone call. See FOLLOW UP Consent. Patients will not be compensated for participation. We will then ask Subjects for their best phone number(s) to reach them for a follow-up phone call. Sites will maintain a separate password protected database of subject IDs and follow up phone #s. Patients may agree to a phone call and not the EHR review, or vice versa. In those cases obtain the relevant consent, and note that they have accepted only one or the other.

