We will also ask for 1-month follow up in those subjects who said YES to accepting the Covid vaccine in the ED and did not get the vaccine in the ED. We will attempt to get full **written** informed consent for review of their records and phone call at 1 month in the same manner as above.

- **Community Covid Vaccine Information for patients saying No to Vaccine in ED**

Additionally, if the patient says no to accepting the vaccine in the ED today, the CRC will also ask, "*Would you like some information about where you can get a Covid vaccine outside of the emergency department?*" If the patient says yes, then the CRC will provide information about where they can get a Covid vaccine outside of the ED (community locations).

- **Primary Outcomes and Ascertainment**

Our primary outcome for Specific Aim III is **vaccine acceptance at the time of SECOND SURVEY** (the converse of vaccine hesitancy) defined as a response of "yes" to the question "*Would you accept the Covid vaccine in the emergency department today if your doctor asked you?*" This and other outcomes for Specific Aim III will be ascertained during the SECOND SURVEYS at the end of their index ED visit. **If the patient says yes, the CRC will then ask the patient if it is acceptable for them to notify the provider and confirm their receipt of the vaccine.** If the patient says yes, the CRC will notify the provider that they are willing to get the vaccine. CRCs will later confirm with the provider that the patient received the COVID-19 vaccine in the ED.

Our primary outcome for specific aim IV will be **uptake (receipt) of a COVID-19**

vaccine (at any vaccination location) within 28 to 32 days after their index ED visit. For ascertainment of this primary outcome:

- As above, for patients who stated they would accept it in the ED today, CRCs will confirm whether the patient received the vaccine directly from providers or by review of that patient's EHR the following day.
- For those who do not accept the vaccine in the ED **and consent to follow up:** We will conduct EHR review and follow-up phone calls (*Have you received a COVID-19 vaccine?*) one month after index ED visits.

- **28 to 32 Day Follow-Up for Ascertainment of Primary Outcomes**

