CRCs will review Master Data Flow daily (workdays) to determine which subjects have reached the 28-day follow-up time period. The CRC will conduct the first follow-up EHR review and, if necessary, follow up phone call attempt on that 28th index day. For the subsequent second and third EHR reviews and follow-up phone calls, CRCs will use the following weekday calendar, which will ensure no greater than 32 days between the index visit and final outcome ascertainment:

Index Study Visit Day of Week	First Call (Same day of week as index study visit – 4 weeks later)	Second Call	Third Call
Monday	Monday	Tuesday	Wednesday
Tuesday	Tuesday	Wednesday	Thursday
Wednesday	Wednesday	Thursday	Friday
Thursday	Thursday	Friday	Monday
Friday	Friday	Monday	Tuesday

Study subject's medical record #s and telephone #s will be accessed from the **PROCOVAXED Follow up sheet. The CRC who conducts this EHR and phone follow-up will be blinded to the subject's study group assignment (intervention vs non-intervention), i.e., a separate CRC who does not recruit at that site will conduct this phone follow-up.**

- The CRC will first review the EHR to determine whether there is any record of a Covid vaccination in the preceding time period from the study index visit. If there is a record of vaccination, the CRC will record what date and where the study received it. See **Follow up Data Collection** form.
- If there is no record of vaccination in the EHR, the CRC will proceed with a phone call to the study subject. See **Follow up Data Collection** form. CRCs will enter follow up data on both the Master Data Flow and Follow up spreadsheets

via REDCap links.

- If the patient does not answer the phone that morning, the CRC will place two more calls to the study subject over the next 2 workdays. They will vary the time of these calls to improve response.
- If the patient does not answer the phone by the third call, the CRC will leave a message with the phone # of the study team. No more calls will be initiated by the study team after this third call.
- If there is no call received from the study subject one week after the 3rd call, the phone follow up will be considered as incomplete.

Of note, CRCs will only review EHR and conduct phone follow-up with study subjects who have given written consent for these follow-up techniques.

In terms of final ascertainment of Specific Aim 4 (uptake of Covid Vaccine within 28 to 32 days of index ED visit), we will use the following scheme:

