	Any of the following:
Yes, Covid vaccine received	
• Confirmed receipt of Covid vaccine during index ED visit• Confirmed receipt of Covid vaccine via EHR review• Confirmed receipt of Covid vaccine via phone follow-up call

	
All of the following:
 
 • Did not receive Covid vaccine in ED during index visit • Did not receive Covid vaccine on EHR review • Did not receive Covid vaccine on phone follow-up call 
No, Covid vaccine not received
 
**If subject did not receive Covid vaccine in the ED, these 2 scenarios will also qualify as Covid vaccine not received:
 
 • Did not received Covid vaccine on EHR review but unable to complete phone follow-up • Did not received Covid vaccine on phone follow-up but unable to complete EHR review
Indeterminate	Unable to review EHR and Unable to contact subject via phone call

- **Data Recording and Entry**

CRCs will record survey responses and other data via two mechanisms:

- Direct entry into the PROCOVAXED Study REDCap database in real time during surveys via secure links
- Recording onto paper forms first. Then entry of survey information and data after each participant enrollment.

CRCs will keep a running log of all study flow and enrollment, recording on REDCap forms the following data for all patients approached: study date, study arm, “Yes” and “No” to having received a Covid vaccine, “Yes” and “No” agreeing to first surveys, delivery or non-receipt of messaging platforms, agreeing to receipt of study vaccines, receipt of vaccines in the ED, “Yes” and “No” agreeing to follow-up calls and EHR review. See Enrollment Log and Master Data Flow. CRCs will also record First and Second Survey responses on REDCap. Sites are allowed to use either one of two methods for REDCap data entry: recording of survey response on printed sheets and later entering on REDCap, or recording responses in real time directly on REDCap via iPads.

- **Data Analysis**
- **Primary Analysis**

We will compare primary outcomes in patients seen on PROCOVAXED intervention dates with those seen on non-intervention dates to test our 2 study hypotheses. We will measure outcomes in all ED patients surveyed as our group of primary outcome

analysis.

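### Aim IV has no rule for Indeterminate patients; dropping them over-represents ED-vaccinated patients and can bias the odds ratio if the ED share of doses or the follow-up differs by arm

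*Combined protocol and SAP*

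**What the plan says.** - **Outcome classes.** The table closing the section on 28 to 32 day follow-up has three results. Yes needs one confirmed source: the index ED visit, the EHR or the phone call. No can rest on the EHR or the call alone if the other could not be completed. Indeterminate is "Unable to review EHR and Unable to contact subject via phone call".
- **ED doses.** For patients who accept, the Primary Outcomes and Ascertainment section has the coordinator "ask the patient if it is acceptable for them to notify the provider and confirm their receipt of the vaccine". This is spoken permission at the visit.
- **All other outcomes.** For patients who decline, "research staff will ask if they can contact them and review their records in a month for follow up via full written consent". The same written consent is sought from "those subjects who said YES to accepting the Covid vaccine in the ED and did not get the vaccine in the ED". The follow-up section adds that "CRCs will only review EHR and conduct phone follow-up with study subjects who have given written consent for these follow-up techniques".
- **Analysis.** Data Analysis takes all surveyed ED patients as the population and fits a mixed logistic model by maximum likelihood to a yes/no uptake variable. It has no rule for Indeterminate. The only statement on missing data is in the data management plan, which relies on a REDCap quality tool to reduce it.
- **Logging.** Data Recording and Entry lists, for all patients approached, the study arm, "agreeing to receipt of study vaccines, receipt of vaccines in the ED", and agreement to calls and EHR review.

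**The concern.** A patient with no yes/no value cannot enter a binary likelihood, so Indeterminate patients leave the model unless a rule says otherwise. By the table's wording, this group includes patients who refuse both follow-up sources. It would also include patients who miss the second survey, because follow-up consent is requested after it.

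The loss is linked to the outcome. Someone vaccinated in the ED is kept even if they would have refused follow-up; someone vaccinated later, or never, is kept only if follow-up succeeds. The intervention is delivered in the ED, and the Aim III outcome is willingness to take a dose there that day, so a higher ED share of doses in intervention weeks is plausible. A change in where doses are given could then look like a change in one-month uptake, which is a primary outcome. A difference in follow-up between arms could create or hide an effect in the same way.

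**Working it through.** **Inputs from the documents.** Control uptake 15%, target 22%, alpha 0.05, power 0.90, 645 per arm (Sample Size Considerations).

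**Inputs assumed.** The documents do not give:
- ED = proportion of the arm vaccinated in the ED;
- c = share of patients not dosed in the ED whose outcome becomes known.

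Later = p − ED, where p is true uptake. Clustering is ignored, and every ED dose is taken as confirmed.

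**The plan's own figure.** n = [1.960·√(2·0.185·0.815) + 1.282·√(0.15·0.85 + 0.22·0.78)]² / 0.07² = 644.6, so 645 per arm. The stated 1,290 reproduces (two-sided, no continuity correction). It contains no allowance for Indeterminate patients.

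**Formulas when Indeterminate is dropped.**
- Observed rate = (ED + Later·c) / (ED + (1 − ED)·c)
- Observed odds = (ED + Later·c) / ((1 − p)·c)
- Patients kept = 645·(ED + (1 − ED)·c)

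**Step 1: levels.** True 15% vs 22%, ED 5% vs 10%, c = 0.7:
- control 0.120/0.715 = 16.8%
- intervention 0.184/0.730 = 25.2%

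Both are overstated. The OR is 1.67 against a true 1.60.

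**Step 2: no true effect, doses only moved into the ED.** Uptake is 15% in both arms and control ED is 5%. Since (1 − p)·c is the same in both arms, the OR is the ratio of (ED + Later·c). At c = 0.7 and ED 10% this is 0.135/0.120 = 1.125.

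| c | ED 5% vs 10%: OR (two-sided rejection) | ED 5% vs 7%: OR (two-sided rejection) |
|---|---|---|
| 0.9 | 1.04 (5.5%) | 1.01 (5.1%) |
| 0.8 | 1.08 (7%) | 1.03 (5.4%) |
| 0.7 | 1.125 (10.5%) | 1.05 (5.9%) |
| 0.5 | 1.25 (22%) | 1.10 (7.9%) |

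Rejection is for a Wald test of the log OR at 0.05, using the patients kept.

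**Step 3: coding Indeterminate as No.** The rate becomes ED + Later·c. For 5% vs 10%, c = 0.7 gives 12.0% vs 13.5%, OR 1.145; c = 0.5 gives 10.0% vs 12.5%, OR 1.29. For 5% vs 7% the ORs are 1.06 and 1.11. The bias is not removed.

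**Step 4: equal ED share, unequal follow-up, no true effect.** Take c = 0.70 in control and 0.60 in intervention. With 10 of the 15 points given in the ED, OR = (0.130/0.510)/(0.135/0.595) = 1.12; with 5 points, 1.07. With c = 0.90 vs 0.85 the ORs are 1.04 and 1.02. Swapping the arms reverses the direction (0.89 for the first case).

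**Step 5: follow-up related to later vaccination.** Let gY and gN be the known-outcome rates in later-vaccinated and never-vaccinated patients. Observed odds = (ED + Later·gY)/((1 − p)·gN). If gY, gN and the ED share of doses (ED/p) are equal across arms, the factor multiplying the true odds is the same in both arms and cancels: 15% vs 22% with half of doses in the ED returns 1.598 whatever gY is. Bias by this route needs the dependence to differ by arm, or the ED share to differ.

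**Step 6: keeping ED doses and filling in the rest.** Rate = ED + (1 − ED)·P(later dose | not dosed in ED, known). At c = 0.7 with no true effect, control is 0.05 + 0.95·(0.070/0.665) = 15% and intervention is 0.10 + 0.90·(0.035/0.630) = 15%, so the OR is 1.00. This assumes gY = gN among patients not dosed in the ED. If that fails (gN = 0.7, ED 5% vs 10%, no true effect):

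| gY | Dropped OR | Filled-in OR |
|---|---|---|
| 0.49 | 1.26 | 1.13 |
| 0.84 | 1.06 | 0.94 |
| 1.00 | 1.00 | 0.89 |

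Above a gY of about 0.84, dropping is the less biased choice.

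**The case against.** **Intention to treat.** A reader might infer that dropping these patients contradicts the intention-to-treat statement. The documents do not support that: the statement concerns analysis by allocated arm whether or not the messaging was received, which is adherence and not missing outcomes. Taken together, the consent limits, the Indeterminate class and the follow-up wording suggest that only determinate outcomes would be analysed. What is missing is the sentence that says so and deals with the consequence.

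**Existing safeguards.** An EHR review alone gives a Yes or No, so a failed call leaves a patient Indeterminate only when the record could not be reviewed. There are up to three attempts by a coordinator blinded to arm. Both arms get the same acceptance question and provider notification. These could keep c high, and at c = 0.9 the ORs in Step 2 are 1.04 and 1.01. The consent rate, which caps c, is not given.

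**ED supply.** The plan expects ED vaccine for at least the first 6 months of about 50 weeks. If only half of patients could be dosed in the ED (2.5% vs 5%, and 2.5% vs 3.5%), the ORs at c = 0.7 fall from 1.125 to 1.07 and from 1.05 to 1.03. This stands and shrinks the effect.

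**Imputation is not always better.** This also stands (Step 6). It is a reason for sensitivity analyses, not for leaving the rule unstated.

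**Conclusion.** The gap is real: a three-way outcome feeds a two-way model with no rule for the third class. That Indeterminate patients drop out is an inference from this. If they do, and follow-up is incomplete, uptake is overstated in both arms. The OR is biased in three situations:
- the ED share of doses differs by arm;
- some doses are given in the ED and the known-outcome rate differs by arm;
- follow-up depends on later vaccination differently by arm, or in the same way in both arms while the ED share differs.

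If none of these holds, the OR is unbiased. A reader might infer that any link between follow-up and later vaccination biases it; Step 5 shows that an identical link cancels when ED shares are equal.

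In the no-effect illustrations of Step 2, the OR runs from 1.01 (small shift, c = 0.9) to 1.25 (large shift, c = 0.5). A reader might also infer that this trial's Aim IV result is materially biased. The documents cannot show that, since they give neither c nor the ED share. Confidence is high in the missing rule and in the conditional bias, but not in any particular size.

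**What to change.** In the ascertainment table and the Primary Analysis section, state that the Aim IV primary analysis:
- includes all surveyed patients by allocated arm;
- counts confirmed ED doses as Yes;
- multiply imputes, or weights for, unknown outcomes among patients not dosed in the ED, using arm, site, calendar period and survey answers;
- assumes that, given these variables, follow-up is unrelated to later vaccination.

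Treat ED-dose status as unknown, not as No, for acceptors who refuse the ED check and for patients with no second survey. The plan says of acceptors: "They will also ask the patient if they (the CRC) can check to see if the patient receives the vaccine in the ED". The listed log fields do not include the answer, so record it.

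Report Indeterminate and non-consent counts by arm and ED-dose status. Prespecify a complete-case analysis and delta-adjusted analyses with the delta varied separately by arm.

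**Cost.** Analysis work, possibly one added log field, and slightly wider intervals. For true 15% vs 22% with ED doses 5% vs 10%, the standard error of the log OR is 0.165 at c = 0.7, against 0.164 when dropping and 0.146 with complete follow-up. At c = 0.5 the figures are 0.188, 0.181 and 0.146. Power is about 0.875, 0.81 and 0.71 at c = 0.9, 0.7 and 0.5, against 0.90 with complete follow-up. Dropping rejects more often (0.88 at c = 0.7) mainly because its OR is inflated.
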